#### *Measures of Associated Symptoms*

- Aberrant Behavior Checklist (ABC) – Irritability and Social Withdrawal Subscales: The ABC was designed to measure behavior problems in individuals with developmental disabilities and ASD through informant report. The subscales of the ABC include: Irritability, Social Withdrawal, Stereotypic Behavior, Hyperactivity/Noncompliance, and Inappropriate Speech. Items are rated on a 4-point scale (ranging from 0=no problem at all to 3 = problem is severe in degree) (79-81). The ABC has been used in multiple ASD trials to measure changes in irritability and social withdrawal, with success. It will be completed by caregivers at the enrollment/baseline visit (or at the screening visit), the final study visit (Week 6), and 6 weeks after medication discontinuation (optional), and takes approximately 20 minutes to complete.
- Anxiety, Depression and Mood Scale (ADAMS): The ADAMS was developed to provide a psychometrically sound instrument for quantifying anxiety, depression and mood disorders among individuals with intellectual disabilities above age 10 (82). It contains 55 symptom items that resolve into five subscales labeled: Manic/Hyperactive Behavior, Depressed Mood, Social Avoidance, General Anxiety, and Compulsive Behavior. The ADAMS total score was the top-line outcome measure in the previously mentioned pilot trial of CBD in FXS. The ADAMS will be administered at the enrollment/baseline visit (or at the screening visit), at the final

study visit (Week 6), and 6 weeks after medication discontinuation (optional). It takes approximately 10 minutes to complete.

- Anxiety Scale for Children – Autism Spectrum Disorder – Child and Parent versions (ASC-ASD): The ASC-ASD was developed as the first anxiety measure specifically designed to detect symptoms in youth with ASD. Psychometrics of this new measure are promising (83). Both the parent and child versions are 24 items in length, making up four subscales: Performance Anxiety, Uncertainty, Anxious Arousal, and Separation Anxiety. The ASC-ASD-Parent and the ASC-ASD-Child will be administered at the enrollment/baseline visit (or at the screening visit) and final visit (Week 6) and both take approximately 15 minutes to complete. The ASC-ASD-Parent will also be administered 6 weeks after medication discontinuation (optional).
- Computerized Kiddie Schedule for Affective Disorders and Schizophrenia (KSADS-COMP): The KSADS-COMP is a DSM-5 based instrument administered by a secure web-based computer program to parents/guardians derived from the KSADS (85). The responses and the algorithmically determined presumptive diagnoses are then immediately provided for follow-up and clarification, as needed, by a licensed clinician. The KSADS-COMP will be used in the current study to allow for further clinical characterization of the sample and will be administered to caregivers online at the enrollment/baseline visit (or at the screening visit). In Part 2 of the trial, the K-SADS-COMP will be administered at the screening visit and will also be used to confirm the presence of an ADHD diagnosis.
- Home Situations Questionnaire – Modified for ASD (HSQ-ASD): The HSQ-ASD is a 24-item questionnaire that measures behavioral noncompliance in everyday settings for children with ASD (86). The HSQ-ASD is a modified version of the HSQ (87), a measure that was initially designed for assessing noncompliance in children with disruptive behavior disorders. In its modified form, the HSQ-ASD includes an additional 7 items that address a broader range of situations in which children with ASD may display noncompliance and consists of two 12-item factors: Socially Inflexible and Demand Specific. To complete the form, caregivers indicate whether the child has a problem with compliance in each situation and, if so, to rate the severity of non-compliance on a 1–9 Likert scale. Higher scores indicate greater non-compliance. The HSQ-ASD will be completed by caregivers at the enrollment/baseline visit (or at the screening visit) and the final study visit (Week 6), and 6 weeks after medication discontinuation (optional), and takes approximately 10 minutes to complete.
- Screen for Child Anxiety Related Disorders (SCARED), Parent Version: The SCARED, Parent Version is a parent report measure with strong psychometrics developed to measure child anxiety symptoms. Subscales include Somatic Symptoms/Panic Disorder, Generalized Anxiety Disorder, Separation Anxiety, Social Phobia, and School Phobia. Research exists demonstrating the utility of the SCARED for assessing anxiety in the ASD population (88). The SCARED, Parent Version takes approximately 10 minutes to complete and will be administered to parents/guardians at the enrollment/baseline visit (or at the screening visit), at the final study visit (Week 6), and 6 weeks after medication discontinuation (optional).
- The Sleep Disturbance Scale for Children (SDSC): The SDSC is an informant-report measure designed to assess the most common areas of sleep disorders in childhood and adolescence (89). The SDSC has six subscales including Disorders of Initiating and Maintaining Sleep, Sleep Breathing Disorders, Disorders of Arousal, Sleep Wake Transition Disorders, Disorders of Excessive Somnolence, and Sleep Hyperhydrosis. The SDSC takes approximately 10–15 minutes to complete and will be administered to caregivers of participants at the enrollment/baseline visit (or at the screening visit) and at the final study visit (Week 6), and 6 weeks after medication discontinuation (optional).

- Strengths and Weakness of Attention-Deficit/Hyperactivity Disorder Symptoms and Normal Behavior Scale (SWAN): The SWAN is a parent report measure designed to assess symptoms of ADHD in children and adolescents. The SWAN consists of 18 items that make up two subscales (i.e., ADHD-Inattentive and ADHD-Hyperactive/Impulsive). The SWAN takes approximately 10 minutes to complete and will be administered to caregivers at the baseline/enrollment visit (or at the screening visit) and the final study visit (Week 6) and 6 weeks after medication discontinuation (optional) during Part 2 of the trial.
- Vineland Adaptive Behavior Scales, Third Edition (Vineland-3), Parent/Caregiver Form: The Vineland-3 is frequently used to measure adaptive functioning across the areas of communication, daily living skills, socialization, motor skills, and maladaptive behavior (90). The Parent/Caregiver form is an informant-based questionnaire assessing three core domains (i.e., Communication, Daily Living Skills, and Socialization) and two optional domains (i.e., Motor Skills and Maladaptive Behavior). The core domains sum to a total Adaptive Behavior Composite. The Vineland-3 Parent/Caregiver Form was designed to assess the functioning of individuals 3 years of age or older and takes approximately 15 minutes to complete. The Vineland-3 will be administered at the baseline/enrollment visit (or at the screening visit) and the final visit. Because “high functioning autism” is often a misnomer, in that children with ASD with average to above average IQ and language skills often experience substantial functional impairments (96), the Vineland-3 will provide further characterization of the sample in addition to serving as an outcome measure.

#### *General Functioning*

- Autism Family Experience Questionnaire (AFEQ): The AFEQ was developed to measure the impact of autism interventions on family experience and quality of life. Recent research on the AFEQ demonstrated the measure was sensitive to change in response to intervention in young children with ASD (91). The measure includes 48 items that make up four domains: Parent, Family, Child Development, and Child Symptoms. Ratings on each item can also be summed to equal a total score. The AFEQ will be administered to parents at the enrollment/baseline visit (or at the screening visit) and at the final visit (Week 6) and takes about 15 minutes to complete.
- Clinical Global Impression-Severity (CGI-S): The CGI-S reflects clinician impression of the participant’s current severity of illness on a 7-point scale ranging from 1=not at all ill to 7=among the most extremely ill (69). The CGI-S will be completed by the evaluating clinician at the screening visit, and by clinician consensus at the enrollment/baseline visit and the final study visit (Week 6).

Given the extent of the information we are requesting from caregivers, rating scales will be available to complete online from home during the time period between the screening and enrollment/baseline visits, and in the sixth week of treatment up until the final study visit. Caregivers can choose to complete these forms in the clinic or online. Caregivers can choose to complete these forms prior to their child being found eligible for participation, in the case the additional time makes completion of the measures more feasible for the caregiver and scheduling of subsequent visits more efficient. An eligible child will not be administered the study drug until all forms are submitted. If the caregiver does not complete the forms prior to coming to the final study visit, all forms must be completed at the clinic during that visit.

## 8.2 SAFETY AND OTHER ASSESSMENTS

Prior to the in-person portions of the screening visit, patients and caregivers will be consented and an interview will be conducted regarding medical, psychiatric, and treatment history relevant to the

exclusionary criteria virtually over WebEx. If families prefer to do the full visit in person, parents/guardians will then be set up in a room to complete necessary parent-report measures. Otherwise, they will be instructed to complete these online. Child testing will be conducted. The Wechsler Abbreviated Scale of Intelligence, Second Edition (WASI-II) and the Autism Diagnostic Observation Schedule, Second Edition (ADOS-2) or Childhood Autism Rating Scale, 2nd Edition, High Functioning version (CARS-2-HF) will be administered to ensure patients meet inclusionary criteria for ASD symptom score, language requirements, and IQ. The CGI-S will be completed by the evaluating clinician. These tests are discussed below.

### **Screening measures**

- **Autism Diagnostic Observation Schedule – 2 (ADOS-2)**: The ADOS-2 is a diagnostic tool used to document the presence of ASD. During a semi-structured evaluation, the individual is observed in a naturalistic social situation and assessed across areas of social communication, imagination, and RRBs. The ADOS includes four modules for use with different age groups and language levels; Modules 3 or 4 will be used in this study. The appropriate module of the ADOS will be administered by a certified rater at screening (92, 93). If the potential participant has been administered the ADOS assessment in the past and results are documented, given the substantial stability in ADOS scores across time, there will be no requirement to repeat it. The ADOS-2 takes approximately 45 minutes to complete and will only occur at the screening visit. Total scores must be at or above 7 to participate in the study.
- **Autism Symptom Interview (ASI)**: The ASI is a brief interview derived from the Autism Diagnostic Interview-Revised (ADI-R); the ASI offers improved efficiency while maintaining sound psychometric properties (94). The ASI takes approximately 45 minutes and includes questions about current and past symptoms consistent with ASD. The ASI will be used in conjunction with other interviews, scores from the ADOS-2 and SRS-2, and clinical judgment to confirm ASD diagnoses by the DSM-5 diagnostic criteria at the screening visit.
- **Childhood Autism Rating Scale, 2nd Edition, High Functioning (CARS-2-HF)**: The CARS-2-HF is similar to the ADOS and is a commonly used diagnostic tool to document the presence of ASD in children and adolescents over the age of 6 with broadly average IQ and verbal language. Because the ADOS cannot be administered validly over WebEx or when wearing personal protective equipment, we will administer the CARS-2-HF to participants that do not have documentation of a previous ADOS assessment. The CARS offers more flexibility than the ADOS, as the ADOS requires standardized materials and scripted activities. The psychologists on the team were trained by the developers of the CARS on virtual administration of the instrument, and activities completed within the CARS were adapted, so that administration is similar across participants and clinicians. Participants must score in the mild-to-moderate or severe symptoms of ASD range.
- **Computerized Kiddie Schedule for Affective Disorders and Schizophrenia (KSADS-COMP)**: As described above, in Part 2 of the trial, the K-SADS-COMP will be administered at the screening visit and will also be used to confirm the presence of an ADHD diagnosis.
- **Wechsler Abbreviated Scale of Intelligence, Second Edition (WASI-II)**: The WASI-II was designed to swiftly and accurately assess cognitive functioning and has strong psychometric properties (95). The WASI-II, Two-Subtest Form will be administered in this study to obtain data on intellectual ability. This form consists of two subtests (i.e., Vocabulary and Matrix Reasoning) and takes approximately 10-20 minutes to complete. This will only be completed at screening. Estimated IQ must be at or above 80 to participate in the trial. As with the ADOS-2, the WASI-II will not be administered if a reliable and valid IQ assessment was performed by a qualified

professional and was documented within the previous 3 years of the screening visit or when the child was 6 years of age or older.

- Clinical Global Impression-Severity (CGI-S): Information regarding the CGI-S is provided within Section 8.1 Secondary Study Endpoints. Within the screening visit, patients must receive a rating of 4 (Moderately Ill) or higher on the CGI-S to participate in the trial.
- Social Responsiveness Scale, 2nd Edition (SRS-2), School-Age Form: Information regarding the SRS-2 is provided within Section 8.1 Secondary Study Endpoints. Patients must receive a total T-score of 66 to meet inclusionary criteria for participation in the study.

Further, in the case of virtual visits for participants who do not have prior documentation of an ADOS assessment, because confirming a diagnosis of ASD virtually is understudied, we will follow up cases for which clinicians report substantial uncertainty by administering a complete Autism Diagnostic Interview-Revised (ADI-R), the gold standard interview instrument for ASD that takes 1-3 hours to administer.

Following the child testing, the clinician will score the child and parent measures to determine if benchmarks for eligibility were met. If participants continue to be eligible for participation, a medical exam will be conducted. Patients will receive a brief physical exam, vital sign assessment, a blood draw, a urine drug screen, and, if female, a pregnancy test to further evaluate eligibility criteria. In the case of virtual visits, the urine drug screen and pregnancy test if applicable will be mailed to participating families and we will ask parents to collect urine and then test the urine over WebEx with a study team member “assisting” virtually. We will also accept a note from the child’s pediatrician reporting that the child is in good health and is medically cleared to participate, rather than requiring a separate in-person physical exam. We will not collect vital signs during these virtual visits, as we did not detect any differences in heart rate or blood pressure in response to CBD administration in the first cohort of participants. We have also not noted any reports in the literature on such effects. To participate in the study, patients’ vital signs and results from their tests of hepatic and hematologic function must be within the normal range for their age. Specifically, patients with baseline elevations greater than 3 times the upper limit of normal (UNL) in alanine aminotransferase (ALT) and/or aspartate aminotransferase (AST) or elevations of total bilirubin greater than 2 times the ULN will be excluded. Patients will be excluded if they have a positive urine sample results from drug screening indicating presence of THC, opiates, methamphetamine or cocaine. Patients will also be excluded if pregnant. See table listing screening visit below.

Tasks	Assessments	Inclusionary/Exclusionary Criteria
Gather history	Medical History	
 
☒ History of active seizure disorder/epilepsy
 
☒ Known genetic disorder
 
☒ Diagnosis of Rett syndrome or Childhood Disintegrative Disorder
 
☒ Marked sensory impairment (e.g., blindness, hearing impairment)
 
☒ Pregnant or lactating
 
☒ Current use of medications metabolized primarily by CYP2B6, CYP2C8, CYP2C9, CYP2C19, CYP3A4, or CYP2D6 isoenzymes
 
☒ Refusal to remain abstinent or use contraception
 

	Psychiatric History	
 
☒ Current psychiatric diagnosis of bipolar disorder, MDD, psychosis, schizophrenia, PTSD or active suicidality (ideation and plan)
 

		
 
 History of drug abuse in the past 3 months
 

	Treatment History	
 
 Stable interventions (i.e., allied health therapies, behavioral, educational, non-exclusionary antidepressant or stimulant medication/dosing of medication) for 4 weeks prior to randomization/for the duration of the study
 
 Prior treatment with CBD or an endocannabinoid treatment
 
 Current treatment with valproate or clobazam or other antiepileptic medication
 
 Exposure to investigational agent in 30 days prior to randomizations
 

Developmental and Psychiatric Evaluation	WASI-II	
 
 Estimated IQ <math>\geq</math> 80
 

	ADOS-2	
 
 Qualify for administration of Module 3 or Module 4 (Indicating presence of fluent speech)
 
 Meets or exceeds autism spectrum cutoff on ADOS or CARS-2-HF
 

	SRS-2	
 
 Total T-score <math>\geq</math> 66
 

	CGI-S	
 
 Score <math>\geq</math> 4
 

	K-SADS-COMP (Part 2)	
 
 Presence of ADHD diagnosis confirmed by clinician review of K-SADS-COMP results
 

Medical Examination	Physical Exam (Vital Signs, Height, Weight)	
 
 Personal physician provides documentation indicating the participant is in good health to participate in the trial or physical exam results within normal limits or results of physical exam conducted by study PI within normal limits
 
 AST, ALT are less than 3 times the ULN and total bilirubin is less than 2 times ULN
 

	Clinical Labs	
 
 Results that are within normal range for age
 

	Drug screen	
 
 Positive urine sample results from drug screening indicating presence of: THC, opiates, methamphetamine or cocaine
 

	Pregnancy test	
 
 Positive results of pregnancy test
 

Patients' parents/guardians will be notified about eligibility for the study and enrollment procedures within about 1 week following the receipt of all measures. As mentioned, patients will be screened at different times according to each cohort start date. We estimate screening approximately 5 children at a time to secure a cohort of size 3. After a patient is found eligible, the enrollment/baseline visit will be scheduled in accordance with the availability of cohort "slots" and family availability. If more than 8 weeks elapses following their screening visit, we will confirm continued eligibility by scheduling a telephone appointment. This provision for the possibility of extended time allows for an eligible participant to be assigned to a cohort that follows the one they were screened for. This will be important in the case that 5 children were screened for a cohort (as described) but more than 3 were eligible. It could also come into play when the family's anticipated schedule will conflict with trial attendance requirements. A cohort does not need to participate in the trial simultaneously. One or two

children within a cohort of size 3 could begin the trial without all three participants in the cohort having been recruited. This will minimize asking families to defer changes in treatment while waiting for a cohort to be established. Decisions regarding termination or continuation of Part 2 of the trial will still depend on the result of each three participant cohort, even if not performed contemporaneously.

Through the trial, safety will be assessed regularly using the assessment strategies listed below.

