Strengths and Weaknesses of Attention-Deficit/Hyperactivity Disorder Symptoms and Normal Behavior (SWAN)		X*						X			X	
Vineland Adaptive Behavior Scales-3 Parent/Caregiver Form (Vineland-3)		X*						X				

Procedures	Screening	Study Visit 1 Enrollment/Baseline	Telephone Follow-Up 1	Study Visit 2	Telephone Follow-Up 2	Study Visit 3	Telephone Follow-Up 3	Study Visit 4 Final Study Visit	2-Week Post-Trial Telephone Follow-Up	4-Week Post-Trial Telephone Follow-Up	6-Week Post-Trial Follow-Up	3-Month Telephone Follow-Up(s) f
Wechsler Abbreviated Scale of Intelligence, 2 nd Edition (WASI-II)	X											

a: Albumin, alkaline phosphatase, AST, ALT, total bilirubin, LDH, total protein; complete blood count.                      b: Urine pregnancy test (females of childbearing potential)                      c: Parents/guardians will be asked if they can be contacted every 3 months following the completion of the trial to provide data on longer-term behavior changes and parental choice in treatment, including whether they pursued continuation of CBD, for up to 1 year.                      *As in-person visits have transitioned to virtual visits following re-initiation after a pause due to the COVID-19 pandemic, select procedures to be completed in certain cases (e.g., family prefers to attend in-person visit and agrees to in-person procedures; Week 4 blood draw clinically indicated from baseline blood draw results as per clinical judgement of PI)                      *Questionnaires must be completed prior to medication administration; however, caregivers will be given the option to complete them during screening or baseline.
												

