- Subjects who have had changes in allied health therapies, behavioral or educational interventions within 4 weeks prior to initiation of trial, other than those associated with school holidays
- Subjects who have had changes in non-exclusionary psychotropic medications within 4 weeks of initiation of trial

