### *Lifestyle Considerations*

During this study, participants are asked to:

- Refrain from making changes in allied health therapies, behavioral or educational interventions
- Refrain from making changes in non-exclusionary psychotropic medication (e.g., methylphenidate) regimen or dosage
- Abstain from illicit drugs, particularly THC, opiates, methamphetamine and cocaine
- Use abstinence or use a valid method of contraception

If prohibited medication, treatment, or practices are indicated during the trial, the participant will be withdrawn from the trial. Notably, if the patient/caregiver states they plan to discontinue exclusionary medications to participate in the trial, they will be required to do so under the care of their treating physician, and will remain under that clinician's care during the titration/discontinuation and throughout their participation in this study.

Importantly, participants will be screened for contraindications to MRI scanning (e.g., metal implants, pacemakers, metal foreign bodies, pregnancy). They will not be permitted to undergo optional scanning if they meet a condition that is contraindicated.

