- Repetitive Behavior Scale-Revised (RBS-R): The RBS-R is a questionnaire used to measure the range of RRBs expressed by individuals with ASD. The RBS-R consists of six subscales covering a range of RRB subtypes including: Stereotyped Behavior, Self-injurious Behavior, Compulsive Behavior, Routine Behavior, Sameness Behavior, and Restricted Behavior. The subscales have no overlap of item content, permitting differential identification and scoring of discrete varieties of RRB. The presence and frequency of behaviors are rated on a 4-point scale (ranging from 0=behavior does not occur to 3=behavior occurs and is a severe problem) (74-76). The RBS-R will be completed by caregivers at the enrollment/baseline visit (or at the screening visit), at the final study visit (Week 6), and 6 weeks after medication discontinuation (optional), and takes approximately 20 minutes to complete.
- Social Responsiveness Scale, 2nd Edition (SRS-2), School-Age Form: The SRS-2 is a measure of social impairment related to ASD in children aged 4 to 18 years old. Five domains are assessed including: Social Awareness, Social Cognition, Social Communication, Social Motivation, and Restricted Interests and Repetitive Behavior. Items are scored on a 4-point scale (ranging from 1=not true to 4=almost always true). Excellent psychometric properties have been previously established for the SRS for use in children and adults (77, 78). The SRS-2 will be administered at screening and at the final study visit (Week 6), and 6 weeks after medication discontinuation (optional). The SRS-2 takes approximately 20 minutes to complete.

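### When a child's start is delayed, caregiver-rated baselines (always so for SRS-2) can predate the 4-week stability window, so pre-dose change is counted as change on CBD

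*Combined protocol and SAP*

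**What the plan says.** - **Timing of forms.** The Schedule of Activities footnote (Section 1.3) reads: "Questionnaires must be completed prior to medication administration; however, caregivers will be given the option to complete them during screening or baseline". The entries for most caregiver scales in Section 8.1 repeat the option, and the closing text of that section adds: "Caregivers can choose to complete these forms prior to their child being found eligible for participation". The only deadline is that dosing waits until all forms are in.
- **SRS-2.** Sections 1.3 and 8.1 give it one pre-treatment administration, at screening. Its row in the schedule has no baseline-visit entry.
- **Waiting time.** Section 8.2 says that its rule on long waits "allows for an eligible participant to be assigned to a cohort that follows the one they were screened for". The check it sets is: "If more than 8 weeks elapses following their screening visit, we will confirm continued eligibility by scheduling a telephone appointment". It gives no upper limit and asks for no repeat of forms or tests.
- **Stability of other treatment.** Section 5.2 excludes children whose therapies changed "within 4 weeks prior to initiation of trial, other than those associated with school holidays", with a parallel 4-week rule for non-exclusionary psychotropic medication. Lifestyle Considerations also provides for families who "plan to discontinue exclusionary medications to participate in the trial", without saying when this happens relative to the forms.
- **Use of the scores.** Section 9.4.3 reports effect sizes with 95% confidence intervals for change from enrollment/baseline to the final visit, in a single-group trial. Section 6.1.2 makes change in relevant scores one input to the CGI-I consensus.

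**The concern.** In a trial without a control group, the whole difference between the pre-treatment and Week 6 scores is read as change on CBD. That reading is safest when the pre-treatment score is taken close to the first dose, inside the period in which other treatment is held stable. The plan does not ensure this. If a caregiver completes the forms at screening and the child then waits for a later cohort, the score can date from before the stability window opens. For SRS-2 the screening date applies to every child.

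Two uses are exposed. The effect sizes are meant to guide the choice of primary outcome for the next randomized trial (Section 3), and that comparison is distorted if SRS-2 always dates from screening while the other scales vary. The same change scores also feed, less directly, the responder classification on which Part 2 termination rests. Part 2 requires ADHD, allows stable methylphenidate and adds SWAN, so a stimulant adjustment between an early SWAN form and the stability window is a concrete example.

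**Working it through.** The plan gives no figure for this point, so there is none to reproduce. The check is timeline arithmetic.

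**Inputs**
- Treatment period: 6 weeks (Section 1.1).
- Participation: 8 to 10 weeks (Section 1.1). I assume that this runs from screening to the final visit.
- Trial length: about 100 weeks for 10 cohorts (Sections 1.1 and 1.2); Section 5.4 expects accrual in 22 months.
- Stability window: 4 weeks (Section 5.2), read here as 4 weeks before first dose.

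**Gap G from screening to first dose**
- Usual: 8 − 6 = 2 weeks to 10 − 6 = 4 weeks.
- Cohort pace: 100/10 = 10 weeks; from 22 months, about 9.6 weeks.
- Moved by one cohort: the wait grows by about 6 weeks (one treatment period) to 10 weeks (the planned pace), so G is about 2 + 6 = 8 to 4 + 10 = 14 weeks.

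**Consequences for a form dated at screening**
- Time after the form but before the stability window: max(0, G − 4).
- Pre-post interval: G + 6.
- Share of that interval on CBD: 6/(G + 6).

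| G (weeks) | Exposed time (weeks) | Pre-post interval (weeks) | Share on CBD |
|---|---|---|---|
| 2 | 0 | 8 | 75% |
| 4 | 0 | 10 | 60% |
| 8 | 4 | 14 | 43% |
| 10 | 6 | 16 | 38% |
| 14 | 10 | 20 | 30% |

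**Size of the bias.** If a fraction f of children change before dosing and after the form, by d SD on average in one direction, the mean change shifts by f × d. Neither value is in the documents. Assuming f = 0.1 to 0.4 and d = 0.2 to 0.5 gives 0.1 × 0.2 = 0.02 SD to 0.4 × 0.5 = 0.20 SD. For scale, the standard error of a mean change, in units of the SD of change, is 1/√30 = 0.18 for 30 children and 1/√15 = 0.26 for 15.

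**Telephone confirmation against the criteria.** Laboratory results, the urine drug screen and the SRS-2 cutoff (Sections 5.1 and 5.2) rest on tests whose only scheduled pre-dose occasion is screening (Section 1.3). A call cannot re-establish them. On pregnancy testing, Section 2.3.3 asks for a test before study drug starts and before each MRI, whereas Sections 1.3 and 8.3.9 place the test at screening.

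**The case against.** Several stronger readings are tempting, and the documents do not support them.

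- A reader might infer that all secondary results are affected. They are not. CGI-S and OSU Autism CGI-S are rated at the baseline visit, and CGI-I and OSU Autism CGI-I are Week 6 improvement ratings. The individualized target is also set at the baseline visit, and score change is one input to the CGI-I beside clinical judgment and informant report.
- A reader might infer that the call is the only check before dosing. The baseline visit also repeats CGI-S, OSU Autism CGI-S, C-SSRS, vital signs and medication review, and Section 6.5 has therapies reviewed at each contact.
- A reader might infer that the plan expressly lets a child change treatment after the forms are done. The text is ambiguous. Section 5.3 treats a recent regimen change as a reason for screen failure and later rescreening. Lifestyle Considerations asks families to avoid changes during the study, and Section 8.2 implies that some are asked to defer changes while waiting. What stands is that deferral is not required, and that *initiation of trial* is undefined: the screening table in Section 8.2 anchors stability to randomization, which this trial does not have.

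It is also fair that the usual gap leaves no exposed time, that children may start before a cohort is full, that changes in both directions partly cancel, and that early completion is a deliberate way to spare caregivers. All endpoints are declared exploratory. These points limit how often the problem arises. They do not close the gap, because reviewing therapies does not refresh an old score.

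**Conclusion.** The gap is real but confined. It applies to children whose start is delayed, with certainty for SRS-2 and, for the other caregiver scales, only where the forms were completed early. At the planned pace such a child's score could predate the stability window by 4 to 10 weeks, with 30% to 43% of the pre-post interval on CBD. This assumes that participation is counted from screening to the final visit and that the 4 weeks run back from first dose.

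How many children would be delayed, and how far their scores would move, cannot be derived from the documents. The range of 0.02 to 0.20 SD is assumed and could go in either direction; its lower end is negligible, while its upper end is about the size of the standard error with 30 children. The case for acting rests on the timing, which the text establishes, and on how little the remedy costs.

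**What to change.** **Timing.** In Section 8.1 and the Schedule of Activities, including the SRS-2 row, require every caregiver scale used as the pre-treatment value to be completed within the 4 weeks before first dose. Repeat older forms online before dosing. Keep the screening SRS-2 for eligibility. The exposed time then falls to zero for any wait, the pre-post interval is at most 10 weeks, and at least 6/10 = 60% of it is on CBD. Natural change over those last 4 weeks at most would remain.

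**Records and definitions.** Record the form-to-dose interval and any treatment change in between. Define *initiation of trial* in Section 5.2 and use the same anchor in the screening table of Section 8.2.

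**Analysis.** In Section 9.4.3, add a sensitivity analysis for children already enrolled that excludes baselines older than 4 weeks.

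**Reconciliation.** Separately, reconcile the telephone confirmation in Section 8.2 with the criteria in Sections 5.1 and 5.2 that rest on laboratory tests, the urine drug screen and SRS-2. Reconcile the timing of the pregnancy test across Sections 1.3, 2.3.3 and 8.3.9. Which clinical rule should apply is for the investigators.

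**Cost.** Some caregivers repeat questionnaires, about 20 minutes for SRS-2 by the plan's own estimate. The scales need no extra visit, since they are already available online between screening and baseline and dosing already waits for them.
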